## **WP2. Content analysis of clinical guidelines**

The following information will be registered for identified clinical guidelines:

- **General information** on the clinical guideline (name, version number & version date (national level publication), number & version date (only applicable to international guidelines, international level publication) frequency of updating (number/months), website/link, funding reported to be received (yes/no) and country;
  
- Information about the **target audience** of the guideline (coverage [country, regional, other, not specified], setting [primary care, secondary care, both, other, not specified], and medical specialty [general practitioners, neurologists, psychiatrists, oncologists, orthopaedists, internists, geriatricians, endocrinologists, rheumatologists, dermatologists, gastroenterologists, nurses, pharmacists and others), the **population** to whom the guideline applies (children [0-9 years], adolescents [10-17 years], adult [18-64 years], seniors [65 and older], pregnant females, other), and treatment (active substance: valproate, fluoroquinolones), methotrexate, metformin, fluorouracil and related substances) and **therapeutic area** based on approved indications (neurology, psychiatry, diabetes, infections, immunology, oncology, other);
  
- **Information about the RMM** included in guideline: information on case study medication safety mentioned (yes/no), content of safety information (original language and English translation), RMM mentioned (yes/no, see Appendix I, page 31-32), RMM tool mentioned (yes/no), type of RMM tool (SmPC, package leaflet, visual reminders on packaging, HCP guide/checklist, patient guide, patient card, annual risk acknowledgement form, DHCP, and suspension), recommendations in relation to RMM included (yes/no), clinical action related to RMM (yes/no, see list in Appendix I), explicit mention of reference for RMM information (yes/no), reference (in case explicit mention of reference is yes).

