## **WP3. Interviews of key informants**

The following information will be collected in the interviews:

- Updating approach: Continuous updating/Regular updating
- Decision to update
- Updating scope: Full updating/ Partial updating
- Impact of the new evidence
- Signal for an update
- Surveillance process
- Time of validity
- Timeframe for updating
- Tools and resources
- Up to date status
- Update cycle
- Update unit

[figure not shown]

Figure 4. Clinical guidelines updating conceptual domains. (19)

[figure not shown]

Figure 5. Clinical guidelines updating strategic domains. (19)

These items describe central aspects of the clinical guideline updating processes and were identified and defined in recent research from The Guidelines International Network’s Updating Guidelines Working Group (GIN-UGWP) in their framework for the conceptual domains related to updating of clinical guidelines (21). The terms were organized in conceptual domains (time, methods, and unit; see figure 4) and on a continuum from strategic level to concrete task level (i.e., strategic domains; approach, strategy, process, and task; see figure 5).

The findings of this study will be discussed and analysed by geographical region and country (see 9.2.1.), by therapeutic area (see section 7), by special population (pregnancy, elderly), by type of health care provider (primary care, secondary care health care provider, nurse, pharmacist, as appropriate). National context will be accounted for when analysing and interpreting the results. Moreover, collecting the information allows us in the analysis to describe what inhibits, delays, or complicates the process (barriers) and what facilitates and ensures important aspects of the process (enablers).

Documents identified will be classified as either local, regional, or national and in case of publication by international professional organisations at international level.

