	
each patient's potential for becoming pregnant, - pregnancy tests before starting and during treatment as needed, - counselling about the risks of valproate treatment and the need for effective contraception throughout treatment, - a review of ongoing treatment by a specialist at least annually, - introduction of a new risk acknowledgement form that patients and prescribers will go through at each such annual review to confirm that appropriate advice has been given and understood.
	
bacterial (chronic) prostatitis; - for preventing traveller's diarrhoea or recurring lower urinary tract infections (urine infections that do not extend beyond the bladder); - to treat mild or moderate bacterial infections unless other antibacterial medicines commonly recommended for these infections cannot be used. Importantly, fluoroquinolones should generally be avoided in patients who have previously had serious side effects with a fluoroquinolone or quinolone antibiotic. They should be used with special caution in the elderly, patients with kidney disease and those who have had an organ transplantation because these patients are at a higher risk of tendon injury. Since the use of a corticosteroid with a fluoroquinolone also increases this risk, combined use of these medicines should be avoided.
	
-To avoid confusion, recommendations to split the dose should be deleted from the product information for the tablet formulation. -Packaging for all methotrexate-containing medicines for once-weekly use to include a prominent reminder of how the medicine should be used. -Patient card emphasising the weekly dosing for inflammatory diseases to be provided with oral medicines. -Healthcare professionals to be provided with educational materials for oral medicines and to counsel patients accordingly. -Tablets to be available in blister packs instead of bottles (or tubes) in order to help patients follow the once-weekly dosing.
	
possible increased risk in these patients. The contraindication for patients with severely reduced kidney function will remain (GFR less than 30 ml/min). Reduced doses should be considered for patients with moderate reduction of kidney function according to dosage recommendations provided in the updated product information. The product information also details risk factors for lactic acidosis which should be reviewed prior to and during treatment.
	
related medicines, capecitabine and tegafur

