Clinical Action					
	
Contraindicated in girls and women able to have children, unless terms of a special pregnancy prevention programme are fulfilled
	
Avoid therapy in patients who are older
	
Should only be prescribed by physicians with expertise in using methotrexate medicines
	
Reduced dose for patients with moderate kidney function
	
Phenotype and/or genotype testing for DPD deficiency before starting treatment with fluoropyrimidines

	
Assess potential of patient for becoming pregnant
	
Avoid therapy in patients who have renal impairment
	
Give clear instructions to patients about once-weekly dosing
	
Assess patient risk factors for lactic acidosis prior to and during treatment
	
Treatment is contraindicated in patients with complete DPD deficiency (fluoropyrimidines)

	
Pregnancy test before starting and during treatment
	
Avoid therapy in patients who have had solid organ transplantation
	
Check that patients (or carer) understand that the medicines must be used once a
	
Use in patients with GFR<30 ml/min is contraindicated
	
A reduced starting dose should be considered in patients with partial DPD

			week, repeat this check every time the medicine is issued or dispensed		deficiency (fluoropyrimidines)
	Counselling about the risks of treatment and the need for effective contraception throughout treatment	Avoid therapy in patients treated with corticosteroid	Counsel patient (or carer) on signs of methotrexate overdoses and give instructions to promptly seek medical advice in case of suspected overdose	Consider using individual tables in patients with reduced kidney function that use fixed-dose combination products	Therapeutic drug monitoring of fluorouracil in patients receiving continuous fluorouracil infusions
	Review ongoing treatment at least annually	Discontinue fluoroquinolone treatment at the first sign of tendon pain or inflammation or in case of symptoms of neuropathy		Fixed-dose combination dapagliflozin/metformin (Ebymect, Zigduo) are not recommended when GFR<60 ml/min	Pre-treatment testing for DPD deficiency is not required for treatment with flucytosine

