	Go through risk acknowledgement form at each annual review	Do not use in patients who have had a serious adverse reactions associated with quinolone or fluoroquinolone medicines		Fixed-dose combination canagliflozin/metformin (Vokanamet) are not recommended when GFR<45 ml/min	Treatment is contraindicated in patients with complete DPD deficiency (flucytosine)
	Do not start therapy unless alternative treatments are not suitable (including girls below age of puberty)			Fixed-dose combination empagliflozin/metformin (Synjardy) are not recommended when GFR<45 ml/min	Treatment should be stopped in case of drug toxicity (flucytosine)
	Women and girls who have been prescribed valproate should not stop taking their medicine without consultation			Fixed-dose combination canagliflozin/metformin (Vokanamet) should not be started when GFR<60 ml/min	
	If a woman using valproate becomes pregnant, she must be immediately referred to a specialist to re-evaluate treatment with valproate and consider alternative option			Fixed-dose combination empagliflozin/metformin (Synjardy) should not be started when GFR<60 ml/min	
	A patient guide and a patient card should be provided to all women of childbearing potential			In patients with GFR of 60-89 mL/min, maximum daily dose (MDD) of 3000 mg divided in 2-3 doses per day; dose reduction may be considered in relation to declining renal function	
				In patients with GFR of 45-59 mL/min, MDD	

				of 2000 mg divided in 2-3 doses per day	
				In patients with GFR of 30-44 mL/min, MDD of 1000 mg divided in 2-3 doses per day	
				Starting dose at most half of the maximum dose in patients with GFR of 30-59 mL/min”	

\*This table includes the tools for risk minimisation which EMA has considered most relevant to integration in clinical guidelines in their request for information to Member States but does not include a complete list of all RMM tools required by PRAC for the case examples.

\*\* For complete information on overview of the measures taken for each active substance see links below:  
<https://www.ema.europa.eu/en/news/new-measures-avoid-valproate-exposure-pregnancy-endorsed>  
<https://www.ema.europa.eu/en/medicines/human/referrals/quinolone-fluoroquinolone-containing-medicinal-products>  
<https://www.ema.europa.eu/en/news/prac-recommends-new-measures-avoid-dosing-errors-methotrexate>  
<https://www.ema.europa.eu/en/news/use-metformin-treat-diabetes-now-expanded-patients-moderately-reduced-kidney-function>  

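### Appendix I tells WP2 coders that guidelines should avoid fluoroquinolones in three patient groups, including the elderly, where the same table's Measures row asks only for special caution

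*Protocol*

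**What the plan says.** Section 9.3 (Variables, WP2) lists a coded variable "clinical action related to RMM (yes/no, see list in Appendix I"). Section 9.7 then grades how far each information product covers the risk minimisation measure (RMM), using the results of the coding.

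In the fluoroquinolone column of Appendix I, the Clinical Action row opens with "Avoid therapy in patients who are older". It repeats the same instruction for renal impairment, solid organ transplantation and corticosteroid treatment.

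The Measures row in the same column says: "They should be used with special caution in the elderly, patients with kidney disease and those who have had an organ transplantation". Its next sentence turns to corticosteroids and says that "combined use of these medicines should be avoided".

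A further pair concerns patients with an earlier serious reaction. The Measures row says "fluoroquinolones should generally be avoided in patients who have previously had serious side effects with a fluoroquinolone or quinolone antibiotic"; the Clinical Action row says "Do not use in patients who have had a serious adverse reactions associated with quinolone or fluoroquinolone medicines".

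Section 9.3 (end of the WP3 variables) also plans to analyse findings "by special population (pregnancy, elderly").

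**The concern.** Caution and avoidance are different clinical instructions, and the Measures row keeps them apart in consecutive sentences. The Clinical Action row merges them. Because that row is the list coders work from, a guideline that reproduces the protocol's own description of the RMM could be recorded as lacking three of its actions. Faithful uptake would then count as non-uptake under objective 2.

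The protocol gives no rule for caution wording, and national teams collect and analyse material in their own languages. Two teams could code the same advice differently, and the difference would look like a difference between countries, which is a comparison the multiple-case design is meant to make. One of the three items is also the only listed action that mentions older patients.

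**Working it through.** The protocol has no figure of its own to reproduce here. The check compares the two rows of Appendix I and then counts items.

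**1. Fluoroquinolone items side by side**

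| Clinical Action item | Strength in Clinical Action | Strength in Measures | Relation |
|---|---|---|---|
| Older patients | avoid | special caution | contradicts |
| Renal impairment | avoid | special caution | contradicts |
| Solid organ transplantation | avoid | special caution | contradicts |
| Corticosteroid treatment | avoid | avoid | agrees |
| Stop at first tendon or neuropathy signs | stop | not mentioned | no counterpart |
| Earlier serious reaction | do not use | generally avoid | differs in degree |

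**2. Share of the list affected**

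Listed actions, counted from Appendix I: valproate 10 + fluoroquinolones 6 + methotrexate 4 + metformin 13 + fluorouracil and related substances 7 = 40.

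- Contradicted: 3/6 = 50% of fluoroquinolone actions and 3/40 = 7.5% of all actions.
- Actions naming older patients: 1 of 40, and it is one of the three.

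**3. Search for a rule**

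The protocol's text on WP2 coding and grading (sections 9.1, 9.2.2, 9.3, 9.7 and 9.9) contains no statement on how caution wording is matched to an avoidance item. The WP2 coding framework is cited but not reproduced.

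**4. Effect on one test guideline**

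Suppose a guideline copies the fluoroquinolone Measures text word for word.

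*Assumption A: the six items are scored singly with equal weight (not stated in the protocol).*

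| Reading | Items scored yes | Score |
|---|---|---|
| Literal | corticosteroid | 1/6 = 17% |
| Weaker prior-reaction wording accepted | + earlier reaction | 2/6 = 33% |
| Caution accepted, prior-reaction wording not | corticosteroid + three caution items | 4/6 = 67% |
| Both accepted | all but the stopping item | 5/6 = 83% |

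The spread is 5 − 1 = 4 items. Three come from caution against avoidance and one from the prior-reaction wording.

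*Assumption B: one yes/no per guideline.* The corticosteroid item matches on every reading, so the code is yes each time and the change is nil. Under this assumption the code depends on the reading of caution only for a guideline that advises caution in these groups and contains none of the other listed actions.

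**The case against.** The strongest reply is that the coding rule belongs in the WP2 framework. Section 9.1 says that framework was piloted on eligible guidelines and reviewed by consortium members and the EMA, so its absence from a high-level appendix proves little. This stands as a limit: the framework may settle how caution is coded. It does not make the two rows of the table agree.

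Second, the Measures row is a summary whose footnote refers readers to external links for complete information, and the Clinical Action row contains items the summary lacks. The Clinical Action wording might therefore be the accurate one. That is possible. The protocol alone cannot show which row matches the source, and no claim is made here about which is wrong.

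Third, the action entries may be shorthand labels. For metformin, too, the action list drops the qualification that dose reduction is to be considered. The three fluoroquinolone items go further, because they replace one instruction with a stronger one that the Measures row uses for a different situation.

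Fourth, the size of the effect rests on item-level scoring, and other WP2 variables (safety mentioned, RMM mentioned, recommendations included) could still register caution advice. An elderly stratum could also be defined from the separate population field. These points are fair. They restrict the effect to analyses that use the action items.

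Finally, repair is already possible. WP2 records the "content of safety information (original language and English translation"), and section 9.7 allows the framework to be amended after the first documents. That limits the harm and makes correction cheap, but the amendment still has to be made. Section 9.9 says that WP2 works from pre-determined coding values and will not describe qualitatively how RMMs are represented, so the planned analysis would not recover the strength of the advice unprompted.

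**Conclusion.** The concern holds. Appendix I contradicts itself on three fluoroquinolone items, and the stronger version is the one used for coding. A fourth item differs only in degree.

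The problem is confined to 3 of 40 listed actions, but it covers half of the fluoroquinolone list and the sole action for older patients. Under item-level, equal-weight scoring, the coverage of a guideline faithful to the Measures row could be anywhere from 17% to 83%, with three of the four items in that spread due to the contradiction. Under a single yes/no per guideline the effect on that guideline is nil. The protocol does not say which scoring applies, whether the elderly analysis uses the action items, or which row matches the source RMM. Confidence is therefore medium. The point should be fixed because it leaves the coding standard contradictory as written.

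**What to change.** - Check the three items and the prior-reaction item against the source RMM linked in Appendix I. Correct whichever row is wrong so that both give the same strength.
- Code the three items as avoid, caution or absent, using the safety text already extracted, and show that strength when reporting on the elderly.
- If the WP2 coding framework already has a rule for caution wording, refer to it in Appendix I.

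The cost is a wording correction to at most four entries and one coding rule for three items. No new data are needed, because the safety text is held in the original language and in English.

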**Appendix II: Information on approval dates for RMMs received from MS RFI**

Risk minimisation measure	Valproate	(Fluoro-) Quinolones	Methotrexate	Metformin	Fluorouracil & related substances
SmPC updates	DK: Jul 18 GR: Mar 22 LV: Aug-Nov 18 NL: Jul 18 PT: Jun 19 SI: Dec 18	DK: May 19 to Sept 20 GR: Jan 19-Sep 21 LV: Q2 19 NL: Apr 19 to Feb 20 PT: Jun 19 to Jul 20 SI: Apr 19 to Jun 20	DK: Sep 18 to Jul 19/Mar 21 GR: May 19/Apr 20/Jun 21 LV: Jan 20 NL: 20 PT: Jan-Aug 20 SI: Oct 20	DK: May-Dec 17/Nov 19 GR: Oct 20 LV: Q1 17 NL: Dec 16/Jan 17 PT: May 18 SI: Mar 17	
Visual reminder on packaging	DK: Oct 18 GR: May 19 LV: Nov 18-Jan 19 NL: Oct 18 PT: Jun 2019 SI: Dec 18		DK: Sep-Dec 18/Mar 21 GR: Jul 20 LV: Jan 20 NL: Jan 20-Nov 21 PT: Jan-Aug 20 SI: Oct 20		
Healthcare professional guide/checklist	DK: Sep 18 GR: May 19 LV: Nov 18 NL: Nov 18 PT: Nov 18 SI: Nov 18		DK: Mar 20 GR: Jul 20 LV: Sep 19 NL: Oct/Nov 20 PT: Jan20 SI: Mar 21		
Patient card	DK: Sep 18 GR: May 19 LV: Aug-Nov 18 NL: Nov 18 PT: Nov 18 SI: Nov 18		DK: Mar 20 GR: Jul 20 LV: Nov 19 NL: Apr 20 PT: Jan-Aug 20 SI: Oct 20		
Patient guide	DK: Sep 2018 GR: May 19 LV: Nov 18 NL: Nov 18 PT: Nov 18 SI: Nov 18				
Annual risk acknowledgment form	DK: Aug 18 GR: May 19 LV: Nov 18 NL: Nov 18 PT: Nov 18 SI: Nov 18				
Direct HPC (it is noted the DHPCs are disseminated by the marketing authorisation holders, however NCAs	DK: Sep 18 GR: Dec 18 LV: Nov 18 NL: Nov 18 PT: Nov 18 SI: Nov 18	DK: Apr 19 GR: Apr 19 LV: Apr 19 NL: Mar 19 PT: Oct 18 SI: Mar 19	DK: Sep 19 GR: Sep 19 LV: Nov 19 NL: Oct 19 PT: Dec 19 SI: Sep 19		DK: May 20 GR: May 20 LV: Jun 20 NL: May 20 PT: May 20 SI: May 20

could disseminate them further)					
Suspension		DK: - GR: - (susp. 12, NR) LV: - (susp. 19, NR) NL: - (susp. 17, NR) PT: - SI: - (susp. Apr 19, NR)			

\*This table includes the tools for risk minimisation which EMA has considered most relevant to integration in clinical guidelines in their request for information to Member States but does not include a complete list of all RMM tools required by PRAC for the case examples. NR: not registered

***Appendix III: List of organisations that received information on RMM as indicated by MS.***

Country	Organisation
Denmark	Dansk selskab for klinisk onkologi [Danish Society of Clinical Oncology] Dansk dermatologisk selskab [Danish Dermatology Society] Dansk reumatologisk selskab [Danish Society for Rheumatology] Dansk selskab for Almen medicin [Danish Society for General Medicine] Dansk selskab for gastroenterologi og hepatologi [Danish Society for Gastroenterology and Hepatology] Dansk selskab for geriatric [Danish Geriatric Society] Dansk hæmatologisk selskab [Danish Society for Hematology] Dansk pædiatrisk selskab [Danish Society for Pediatrics] DCCG.dk [Danish Colorectal Cancer Group] Dansk selskab for Klinisk Biokemi [Danish Society of Clinical Biochemistry]
Greece	Information not shared by NCA
Latvia	Professional Association of Neurologists, Professional Association of Children's Neurologists, Professional Association of Psychiatrists, Professional Association of Children's Psychiatrists, Professional Association of Pediatricians, Professional Association of General Practitioners (2 associations), Professional Association of Gynecologists and Obstetrics, Professional Association of Internists Professional Association of Urologists Professional Association of Traumatologists Professional Association of Infectiologists Professional Association of Pulmonologists Professional Association of Anaesthesiologists Professional Association of Intensive Therapy Specialists Professional Association of Dermatovenerologists Professional Association of Oculists Professional Association of Dentists Professional Association of Surgeons Professional Association of Midwives, Professional Association of Pharmacists
Netherlands	Geneesmiddeleninformatiebank.nl Nederlandse vereniging voor Neurologie [Dutch Society for Neurology] Nederlandse vereniging voor Psychiatrie [Dutch Society for Psychiatry] Vereniging voor Manisch Depressieven en Betrokkenen [Association for Manic Depressive and Those involved] Epilepsie vereniging Nederland [Epilepsy Association Netherlands] Nederlandse vereniging voor Reumatologie [Dutch Society for Rheumatology] Nederlandse vereniging voor Dermatologie en Venereologie [Dutch Society for Dermatology and Venereology] Nederlandse vereniging voor Gastro-enterologie [Dutch Society for Gastroenterology] Nederlandse vereniging voor Maag-Darm-Leverartsen Nederlandse vereniging voor Medisch Oncologie [Dutch Society for Medical Oncology] Nederlandse vereniging voor Chirurgisch Oncologie [Dutch Society for Surgical Oncology] Nederlandse vereniging voor Radiotherapie en Oncologie [Dutch Society for Radiotherapy and Oncology] Nederlandse Huisartsen Genootschap [Dutch General Practitioners Association] Koninklijke Nederlandse Maatschappij ter bevordering der Pharmacie [The Royal Dutch Society for the Promotion of Pharmacy] De Nederlandse Vereniging voor Ziekenhuisapothekers [Dutch Society for Hospital Pharmacists]
Portugal	Information not shared by NCA
Slovenia	Medical Chamber Association of Gynecologists and Obstetricians Association for Outpatient Gynecology Section of Gynecology and Obstetrics Trainee Specialists

Pediatric Association Section of Pediatric Neurology Neurologist Association Psychiatrists Association Association for Child and Adolescent Psychiatry Section of Psychiatry Trainee Specialists Association of General Practitioners Chamber of Pharmacists
---

